After consent, participants will be allocated to courses depending on their availability in relation to the dates of the courses. A computerised system will be used within Sheffield Clinical Trials Unit in order to randomise 48 DAFNE courses to either MDI or CSII courses across the 8 participating sites. The randomisation for courses will be stratified by site. Within each centre the first four courses will be randomised in pairs (one MDI, one CSII). The remaining courses will be randomised by minimisation. PIs/Educators will attempt to have allocated 7 individuals to each course at least six weeks prior to the course commencing. By this time, the CTRU will inform the centre whether the course has been allocated as a CSII course or as an MDI course and confirm the allocation of a course number. The PIs and educators will have been blinded to the type of course being delivered until four to six weeks before the course commences and staff within the trials unit will be blinded to the identity of those participating. The participant will find out which course they are allocated to four weeks prior to the DAFNE course. Once the course number has been allocated to the course and the type of course is known to the site, further participants will only be allocated to the course in the situation described below.

If for any reason participants are unable to take part in the course at short notice, they will only be able to participate in the same arm of the study as the course they were originally allocated to. The patient will be given possible dates for the next relevant course and will be informed when that course is due to commence as soon as the PI/educator finds out.

In order to maximise recruitment for the courses, the PI's and educators will be able to invite a new participant to take the place of somebody unable at attend. This will occur only where there is a list of reserve participants in place, prior to the time when the course allocation has been revealed to the educators. In this case, the next person on that list would be invited to participate in that arm of the study. The patient will be allocated a screening number at the point at which they have been invited to participate and have had the inclusion/exclusion criteria check. This screening number will be used to assess the next person on the list.

7. Trial Treatment

Insulin

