It is generally accepted that a difference of 0.5% in HbA1c is clinically worthwhile. To detect this difference with an SD of 1% at 80% power and 5% two sided significance using a t-test requires 64 patients per group for subjects \geq 7.5% (58mmol/mol) HbA1c. In order to allow for a clustering effect of the educators and a within-course intra-class correlation coefficient (ICC) of 0.05, which is common in diabetes care, the sample size increases to 84. Allowing also for a 10% drop out, the sample size per group becomes 93. Audit of the DAFNE database shows that 75% of subjects have an HbA1c of over 7.5% (58mmol/mol). With this in mind we require 124 subjects per group, i.e. 248 in total. We plan to recruit 280 subjects which increases the power to 85% but which allows for some variation in drop-out rates and the proportion of

patients with HbA1c ≥7.5% (58mmol/mol).

We believe that we should include patients who experience frequent hypoglycaemia but who might have existing levels of HbA1c that are near the target range since they may reduce hypoglycaemic episodes and can therefore still provide important information about quality of life. Yet, since there will be no change in HbA1c levels for these participants, including this data would reduce our statistical power to establish improvement in our primary endpoint. We will therefore stratify those entering the trial based on HbA1c levels of $\geq 7.5\%$ (58mmol/mol). The trial will be powered on the number of participants with an HbA1c $\geq 7.5\%$ (58mmol/mol), in whom a fall would reflect worthwhile improvements in glycaemic control but we will also calculate the number of participants in each group who achieve a HbA1c <7.5\% (58mmol/mol).

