In August 2012, a review of recruitment and retention to the trial took place. Recruitment to the trial was on target and most DAFNE courses were allocated with at least 7 participants (planned number of participants per course). However, a number of participant withdrawals (18 from 168 randomised) had also occurred post-randomisation but pre-DAFNE course delivery. The intention-to-treat population is participants who consent to take part in the trial **and** who attend their DAFNE course at least in part. As such participants recruited to the study who do not attend their DAFNE course do not count in the ITT population.

The study sample size of 280 participants allows for a $\leq 10\%$ drop-out rate during the year follow-up. The current rate of participant withdrawal which has occurred exclusively prior to DAFNE course delivery is 11% and the mean number of participants per course is 6. The trial statistician undertook a review to determine the need for additional courses to maintain the study power based on the current drop-out rate. Scenarios were modelled based on current and predicted HbA1c population prevalence ($\geq 7.5\%$) drop-out rate (10% or 15%) and size of

DAFNE course (4, 5, 6 or 7 participants). Assuming these variables remain similar to what has been currently observed (as of August 2012), the trial will need to run an additional two to seven courses in order to maintain power to determine the primary outcome.

Therefore, more than 280 participants will be recruited to the trial to replace participants who drop-out prior to attending their DAFNE course. The number of participants recruited will not exceed 340; however there will be no more than 280 in the ITT population.

As the last two course pairs run at a site, reserve participants who can step in to fill drop-out participant places should they occur on either of the last two courses to ensure these courses run with sufficient numbers of participants.

Data Analysis

An intention to treat analysis will be used primarily but the effect of switching to a per protocol analysis will also be explored.

Primary Analysis

The primary analysis will be a linear model of HbA1c at 2 years with baseline HbA1c as a covariate, (which will improve the power relative to the predicted power). Generalised estimating equations (GEE) will be used to control for clustering within course.

Secondary Analysis

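### The stated primary model leaves out site, although courses are randomised within site: no bias, but the interval tends to be somewhat too wide if sites differ

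*Protocol*

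**What the plan says.** Protocol section 6 (Randomisation) makes the course the randomised unit. A computer system is to "randomise 48 DAFNE courses to either MDI or CSII courses across the 8 participating sites", and "The randomisation for courses will be stratified by site". At each centre the first four courses are allocated as MDI/CSII pairs. For the later ones, "The remaining courses will be randomised by minimisation"; the minimisation factors are not named.

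Protocol section 9 (Primary Analysis) commits to a model, a covariate and a clustering unit: "The primary analysis will be a linear model of HbA1c at 2 years with baseline HbA1c as a covariate". It adds: "Generalised estimating equations (GEE) will be used to control for clustering within course". Site does not appear. No variance estimator, small-sample correction or reference distribution is given, and the end of the Data Analysis section leaves further detail to a statistical analysis plan.

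Two other statements bear on the point. The Sample Size section inflates the numbers "In order to allow for a clustering effect of the educators" and for a within-course intra-class correlation (ICC) of 0.05. After the August 2012 review, "the trial will need to run an additional two to seven courses in order to maintain power".

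**The concern.** Pairing courses within a centre means that anything shared by the centre (case mix, local care, teaching staff) falls on both arms alike and mostly cancels from the treatment difference. With 8 sites and four paired courses each, this covers at least 32 of the 48 courses by construction.

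The stated model sees only courses. Two courses at one centre are treated as independent, and the site differences between them go into the between-course variance from which the standard error is built. The estimate is then more precise than its standard error says.

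The Sample Size section's reference to educators points the same way. If the same educators teach several courses at a centre, which 48 courses over 8 sites suggests but the protocol does not state, courses within a site are correlated.

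At stake is the calibration of the confidence interval for the primary endpoint, and some power.

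**Working it through.** **The plan's own figures.** Difference 0.5, SD 1, 80% power, two-sided 5%, t-test: 64 per group. Design effect 1 + (7 - 1) x 0.05 = 1.30, and 64 x 1.30 = 83.2, given as 84. Then 84/0.9 = 93.3, given as 93, and 93/0.75 = 124 per group, or 248 in total. At 280, the effective number per arm is 140 x 0.75 x 0.9/1.30 = 72.7, with power 84.9% (t) against the stated 85%. The chain reproduces and does not depend on the point made here.

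**Inputs for the check.** 48 courses, 8 sites and 6 courses per site, all balanced within site (a simplification, since later courses are minimised). Evaluable participants per course: 280 x 0.75 x 0.9/48 = 3.9, taken as 4. Course variance 0.05, total variance 1. The site share of variance is not in the protocol and is *assumed* to lie between 0 and 0.10.

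**Closed form, equal courses of m = 4.** Write s, c and e for the site, course and residual variances.

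- True variance of the arm difference: (4/48)(c + e/m). Site cancels.
- Expected plain sandwich variance without site: about (4/48)[(7/8)s + (23/24)(c + e/m)].

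- s = 0, e = 0.95: true SE = sqrt(0.08333 x 0.2875) = 0.155; reported 0.155 x sqrt(23/24) = 0.152, about 2% too small.
- s = 0.05, e = 0.90: true SE = sqrt(0.08333 x 0.275) = 0.151; reported sqrt(0.08333 x (0.0438 + 0.2635)) = 0.160, about 6% too large.
- s = 0.10, e = 0.85: true SE = sqrt(0.08333 x 0.2625) = 0.148; reported sqrt(0.08333 x (0.0875 + 0.2516)) = 0.168, about 14% too large.

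**Simulation with varying course sizes** (exchangeable GEE, 3,000-5,000 null runs, Monte Carlo error 0.3-0.4 points). Columns 2 and 3 are the stated model with a plain sandwich and z reference. The last column uses the Kauermann-Carroll correction with t on 39 df.

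| Site share | Mean SE / true SD | Null rejection | Site added, plain, z | Site added, corrected, t |
|---|---|---|---|---|
| 0 | 0.151 / 0.153-0.154 | 5.8-6.0% | 8.6-8.8% | 4.9% |
| 2% | 0.154 / 0.154 | 5.7% | 9.1% | not run |
| 5% | 0.161 / 0.152-0.153 | 3.8-4.3% | 8.8-9.1% | 5.2% |
| 10% | 0.168 / 0.152 | 3.6% | 9.1% | not run |

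The SE is thus 5-6% too large at a 5% site share and about 10% too large at 10%. A second simulation under its own settings gave about 8% and 12%, with null rejection of 4.1% and 2.8%. In that run, site plus Kauermann-Carroll and t stayed at 4.6-4.9% throughout.

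**Power for 0.5, corrected variance and t in both models.** No site variance: 86.6% without site in the model, 86.2% with it. Site share 5%: 85.7% without, 88.7% with, a gain of 3 points.

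**If the planned ICC of 0.05 already includes site.** Splitting it site/course as 0.02/0.03 or 0.03/0.02 gives null rejection of 5.1% and 4.9% for the stated model with a plain sandwich, and an SE within 3% of the truth.

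**The case against.** Several objections have force.

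- **The site variance is assumed.** Adding 0.05 or 0.10 to a course variance of 0.05 makes the within-course correlation 0.10 or 0.15, two to three times the planning value. HbA1c is also measured in a central laboratory, which removes one source of site differences. This stands: the size is conditional, and it vanishes if the planned ICC already contains site.
- **The design is only partly as modelled.** Pairing covers four courses per centre, and with two to seven more courses there would be about 50-55 clusters. This stands, but does not change the direction.
- **The detail can wait for the analysis plan.** This is right for the variance estimator, but less so for site. The protocol fixes the covariate itself, and an analysis plan that followed it literally would omit site.

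A reader might go further and infer that the protocol uses GEE without a small-sample correction, so that its standard error is wrong. The text does not say so. It is silent on the estimator, and that silence is not an error. Even with a plain sandwich, the two influences oppose each other: omitting a balanced factor widens the interval, while few clusters narrow it slightly. The 8-9% type I error belongs to a model the protocol does not propose, namely site added without a correction.

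**Conclusion.** The stated primary model does not match the randomisation: site stratifies the courses but is absent from the analysis. The treatment estimate is not biased. Under an assumed site share of 5-10% of the variance, the SE is about 5-12% too large, null rejection is about 3-4%, and a few points of power are lost (3 points at a 5% share, like for like). With site variance near zero, or contained in the ICC of 0.05, nothing of note changes. The error is mostly conservative and its size rests on a variance the protocol does not give, so the documents do not support a claim of inflated type I error in the stated analysis. Severity is minor. It is worth correcting because the change costs almost nothing and keeps the interval calibrated whatever the site variance proves to be.

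**What to change.** State the primary model as 2-year HbA1c on arm, baseline HbA1c and site (fixed, 8 levels), by GEE with exchangeable correlation within course. In the same sentence, specify a small-sample corrected variance and a t reference on courses minus parameters: 48 - 10 = 38 df. The simulation's 39 df left out the participant-level baseline term, and the difference is immaterial.

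Kauermann-Carroll is the better calibrated choice here. Mancl-DeRouen is also valid but conservative: with site in the model and t on 39 df it gave null rejection of 2.6-3.0% and power of 79.8-83.4%. The two changes belong together, because site alone with a plain sandwich and z would make matters worse.

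Add site to the secondary GEE models as well, choosing a correction suited to each. What serves the linear models does not carry over automatically to the Poisson or zero-inflated Poisson models for hypoglycaemia.

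The cost is a wording change and seven extra parameters, with no new data. If sites do not differ at all, the loss of power is about 0.4 points (86.6% to 86.2%), within simulation error.

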HbA1c is a measurement of glycosylated haemoglobin which reflects overall blood glucose values over the previous 6-8 weeks(24). This is regarded as the gold standard measure of glycaemic control. There is a strong relationship between HbA1c and the risk of developing long term diabetic complications and it is accepted as a surrogate for long term outcomes in individuals with diabetes(25). With this in mind, the primary endpoints for the trial will be:-

• The change in HbA1c after 2 years in those participants whose baseline HbA1c was at or above 7.5% (58mmol/mol).

Since HbA1c can be measured by different techniques we will ensure standardisation by measuring HbA1c in blood samples at a central laboratory.

Secondary Endpoints

The secondary endpoints include the following:

Demographic measures

Biomedical Endpoints

a) The proportion of participants reaching the NICE target of an HbA1c level of 7.5% (58mmol/mol) or less

- b) Hypoglycaemia (severe & moderate)
- c) Insulin dose
- d) Body weight
- e) Blood lipids & proteinuria
- f) Diabetic Ketoacidosis

Ancillary Study Endpoints

Quantitative

- a) Quality of life (DSQOL, WHOQOLBREF, SF12, EQ5D)
- b) Fear of hypoglycaemia
- c) Diabetes Treatment Satisfaction
- d) Emotional Wellbeing
- e) Adherence to DAFNE principles
- f) Use of bolus calculators
- g) Use of pump features

Qualitative

- a) Participant views regarding the pump/multiple injection course & treatment
- b) Educator views regarding the pump/multiple injection course & treatment

Health Economic

- a) Incremental cost-effectiveness ratio
- b) Sensitivity analyses

Demographic Measures

We will collect demographic measures from participants so that we are able to check the sex, age, ethnicity and socioeconomic status of the trial population and assess whether we have recruited a representative sample.

Biomedical Endpoints

Hypoglycaemia

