Hypoglycaemia is a major side effect of insulin treatment, which prevents many patients from achieving target glucose levels. CSII has been shown to reduce hypoglycaemia in some studies but since DAFNE and similar educational interventions are also associated with reduction in severe episodes we may have insufficient power to detect a difference in the rate of severe episodes between the two groups. During the last NICE appraisal of CSII, the question of the impact of moderate hypoglycaemia was raised. The point was made that moderate hypos, sufficient to interrupt activities of daily living, might because of greater frequency, have more cumulative effect on quality of life than severe hypos. Furthermore, moderate episodes are likely to be more frequent than severe events. We will therefore record both severe and moderate episodes of hypoglycaemia in participants. This should increase power and identify the ability of CSII to reduce rates of hypoglycaemia. It will also be possible to assess the effects of both, by comparing quality of life measures in those with only moderate hypos, versus those with moderate and severe.

Severe hypoglycaemia – any episode leading to cognitive impairment sufficient to cause either coma or requiring the assistance of another person to recover (27).

Moderate hypoglycaemia – any episodes which could be treated by that individual, but where hypoglycaemia caused significant interruption of current activity, such as having caused impaired performance or embarrassment or having been woken during nocturnal sleep.

Insulin dose

Some studies have indicated that CSII results in the use of less insulin. We will therefore record participants' self-reported insulin dose at each time point and calculate units/kg body weight.

Body Weight

If CSII treatment results in the use of less insulin, it may have a favourable effect on weight since with less insulin there is a propensity for the body to store fewer nutrients. We will therefore record weight at each time point of the trial.

Lipids and proteinuria

A recent study (26) reported little difference in HbA1c for CSII compared to MDI but found less progression to microalbuminuria in the CSII group, and also lower cholesterol and lower insulin dose.

Blood samples will be taken using local labs and lipids (including HDL cholesterol). Albumincreatinine ratio (a sensitive measure of proteinuria) will be measured from urine samples.

Diabetic-Ketoacidosis

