Time Period of Study	Collection Tool	When Sent/Given to Patient	When Collected	Who Collects	Which Element(s) of the Trial Relevant for	What Outcome is Covered
Recruitment	Screening Questionnaire	At time of recruitment conversation (phone or face- to-face)	At time of recruitment conversation (phone or face- to-face)	PIs/Educators approaching patients for recruitment	All	If there are problems with recruitment we can understand why and try to rectify
Recruitment	Inclusion/Exclusion Checklist	At time of recruitment conversation (phone or face- to-face)	At time of recruitment conversation (phone or face- to-face)	Pls/Educators approaching patients for recruitment	All	To ensure correct protocol deviations and violations are avoided
Recruitment	Invitation letter/email with screening & Patient Information Sheet	Sent out at time of recruitment	Returned by participant if willing	PIs/Educators approaching patients for recruitment	All	If there are problems with recruitment we can understand why and try to rectify
Baseline	Informed Consent Sheet - includes full participant contact details	See informed consent process diagram	See informed consent process diagram	Pls/Educators	All	To ensure all participants have consented appropriately
Baseline	Trial CRF	Baseline Visit	Baseline Visit	Educators	Biomedical measures	HbA1c, body weight, lipids & proteinuria, diabetic ketoacidosis, severe hypoglycaemic episodes
Baseline	Baseline Hypo Recall Log	Baseline Visit	Baseline Visit & Course Visit	Educators	Biomedical measures	12 months severe hypo recall & 4 weeks moderate hypo recall
Baseline	Instructions for recording hypos	Baseline Visit	Not collected	Educators	Biomedical Measures	Severe and moderate hypoglycaemic episodes

Time Period of Study	Collection Tool	When Sent/Given to Patient	When Collected	Who Collects	Which Element(s) of the Trial Relevant for	What Outcome is Covered
Baseline	Blood and urine samples	Baseline visit	Baseline visit	Laboratory	Biomedical measures	HbA1c, lipids & proteinuria, albumin-creatinine ratio
Baseline	Demographic questionnaire – (in baseline psychosocial pack)	Baseline visit	Course Visit	Educators	Quantitative psychosocial	Demographics
Baseline	WHOQOL-BREF (in psychosocial questionnaire pack)	Baseline visit	Course Visit	Educators	Quantitative psychosocial	Generic quality of life
Baseline	DSQOL (in psychosocial questionnaire pack)	Baseline visit	Course Visit	Educators	Quantitative psychosocial	Diabetes specific quality of life

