Post 6 Months, 1 year, 2 year	Post diary instructions	Sent out 4 weeks prior to 6 month, 1 year & 2 year visits	Not collected	Educators	Biomedical measures	Moderate hypoglycaemic episodes for next 4 week period
Post 6 Months, 1 year, 2 years	Post hypoglycaemia recall log	6 month, 1 year & 2 year visits	6 month, 1 year & 2 year visit	Educators – filled out in conjunction with diary	Biomedical measures.	Moderate hypoglycaemic episodes for preceding 4 week period
Post 6 Months, 1 year, 2 years	Blood and urine samples	6 month, 1 year & 2 year visits	6 month, 1 year & 2 year visit	Laboratory	Biomedical measures	HbA1c & lipids, proteinuria & albumin-creatinine ratio at 1 and 2 years but not 6 months
Post 6 Months, 1 year	Post Psychosocial questionnaire pack (see entries for baseline pack above for separate questionnaires included except for exclusion of baseline demographics and change to DTSQc questionnaire at 1 year)	Sent out approximately 2-6 weeks prior to 6 month & 1 year visits	6 month & 1 year visit	Educators	Quantitative psychosocial, health economics	See entries for baseline pack above for all outcomes covered

Time Period of Study	Collection Tool	When Sent/Given to Patient	When Collected	Who Collects	Which Element(s) of the Trial Relevant for	What Outcome is Covered
Post 2 years	Post Psychosocial questionnaire pack (see entries for baseline pack above for separate questionnaires included) except for the following changes: - Exclusion of baseline demographics - Inclusion of DAFNE principles, use of bolus calculators and use of pump features	Sent out approximately 2-6 weeks prior to 2 year visit	2 year visit	Educators	Quantitative psychosocial, health economics	All outcomes included in the psychosocial questionnaire pack with the addition of: - DAFNE principles - Use of bolus calculators - Use of pump features
Ongoing collection	Severe hypoglycaemia episodes log	Ongoing collection by telephone and CRFs at each visit	Ongoing collection by telephone and CRFs at each visit	Educators – filled out in conjunction with diary	Biomedical measures.	Severe hypoglycaemia episodes throughout duration of the trial
Ongoing collection	AE Identification log	Ongoing collection by telephone and CRFs at each visit	Ongoing collection by telephone and CRFs at each visit	Educators	Biomedical measures	Safety endpoints

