Linear models of insulin usage, body weight, lipids and proteinuria will also be analysed at 2 years with baseline measures as covariates. We will use Poisson regression (or a zero-inflated Poisson regression if necessary) on the number of hypoglycaemic episodes in 2 years, which should also have more power than an analysis based on dichotomy of having experienced/not experienced an episode. Again, GEE will be used for these analyses to account for clustering.

Subgroup Analyses

The analyses outlined above will also be completed for sub-groups stratified at baseline by participants with HbA1c level < and \geq 7.5% (58mmol/mol).

Primarily data will be analysed with missing data excluded. A secondary analysis will also be included using multiple imputation.

Quantitative Psychosocial Analysis

All variables will be subject to statistical analysis. Descriptive and inferential statistical analysis will be conducted using T-tests and ANOVA to compare means, crosstabs to explore individual variables, non-parametric tests including chi-square, correlational analysis and possibly multiple regression analysis. Statistical significance will be defined as $p \le 0.05$ with 95% confidence intervals.

Primarily data will be analysed with missing data excluded. Secondary analyses will also be completed with a) a mean score for each missing questionnaire and b) a minimum score for each missing questionnaire.

A full Statistical Analysis Plan will be submitted at a later date in order to detail this section of the protocol.

10. Trial Supervision

Three committees are being established to govern the conduct of the study:

- 1. Trial Management Group (TMG)
- Trial Steering Committee (TSC)
 Data Monitoring and Ethics Committee (DMEC)

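### The only stated hypoglycaemia analysis models a two-year episode count, but moderate episodes are recorded only in three 4-week windows, so that count cannot be formed for them

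*Protocol*

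**What the plan says.** All references are to the Protocol.

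- **Endpoint.** Section 3, Secondary Endpoints, lists one biomedical endpoint for hypoglycaemia, covering severe and moderate episodes. The Hypoglycaemia paragraph defines the two types separately, concedes that power for severe episodes may be insufficient, and gives this as the reason for recording moderate ones: "This should increase power and identify the ability of CSII to reduce rates of hypoglycaemia".
- **Collection of severe episodes.** Section 8, Table 1, has an ongoing log covering "Severe hypoglycaemia episodes throughout duration of the trial".
- **Collection of moderate episodes.** Table 1 has a recall log for "Moderate hypoglycaemic episodes for preceding 4 week period", completed at the 6-month, 1-year and 2-year visits. The matching diary instructions are "Sent out 4 weeks prior to 6 month, 1 year & 2 year visits".
- **Baseline.** Table 1 has a baseline log for "12 months severe hypo recall & 4 weeks moderate hypo recall".
- **Analysis.** Section 9, Secondary Analysis, states the only hypoglycaemia model: "We will use Poisson regression (or a zero-inflated Poisson regression if necessary) on the number of hypoglycaemic episodes in 2 years", with GEE for clustering. Baseline covariates are named in the preceding sentence, for the linear models of insulin use, weight, lipids and proteinuria.
- **Power.** Section 9, Sample Size, gives a detectable difference for severe episodes as a yes/no outcome. It says that smaller differences would be detectable for moderate episodes, without giving a figure.
- **Deferral.** Section 9 says that a full statistical analysis plan will add detail.

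**The concern.** The model's outcome and the data collection do not match for one of the two components of the endpoint. A count over two years presupposes two years of observation. That holds for severe episodes. Moderate episodes are seen only in three short windows, and only one of those falls in the second year.

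Moderate episodes were added to the trial because they are more frequent and should carry more information. If their outcome is not fixed in advance, someone must decide after the data exist whether to use the final window, the sum of the windows, a rate, or an extrapolated two-year figure, and what to do about missed windows. That choice should not be open once results by arm can be seen.

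**Working it through.** **1. The protocol's own hypoglycaemia figure.** Inputs from section 9, Sample Size: 45% v about 25% with at least one severe episode over 2 years, 80% power, two-sided 5%, continuity-corrected chi-squared test, ICC 0.05, 10% drop-out. Course size is 7 (section 7) and the plan is 140 per arm (Trial Summary).

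- Two proportions, 0.45 v 0.25, with continuity correction: 98 per arm.
- Design effect: 1 + (7 − 1) × 0.05 = 1.30, and 98 × 1.30 = 127.4.
- Drop-out: 127.4 / 0.90 = 141.6 per arm, against 140 planned.

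The figure reproduces when 45% is applied to all 140 per arm. It concerns severe episodes as a dichotomy, so the present point does not affect it. There is no corresponding figure for moderate episodes to check.

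**2. How much of the two years is observed for moderate episodes.** Inputs from Table 1: 3 follow-up windows of 4 weeks each. Two years is about 104 weeks.

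| Visits attended | Weeks observed | Share of 104 weeks |
|---|---|---|
| All three | 3 × 4 = 12 | 12/104 = 11.5% |
| Two | 2 × 4 = 8 | 8/104 = 7.7% |
| One | 1 × 4 = 4 | 4/104 = 3.8% |

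The best case is 12 weeks, or 84 days. At least 104 − 12 = 92 weeks are unobserved for every participant.

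**3. Could another data stream fill the gap?** Section 8, Adverse event inclusions and exclusions, says that non-severe hypoglycaemia is not classed as an adverse event. A suddenly noticeable increase in frequency is reportable, but that records a change and not a count. Nothing else in Table 1 collects moderate episodes between windows.

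**4. The two readings of the analysis sentence.**

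| Reading | Severe episodes | Moderate episodes |
|---|---|---|
| Covers both types | Two-year count can be formed | Two-year count cannot be formed |
| Covers severe only | Two-year count can be formed | Named in the endpoint, no analysis stated |

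Under either reading the text needs changing for moderate episodes.

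**The case against.** The best defence is that the sentence means severe episodes. It does not name moderate ones, and it contrasts the count with a dichotomy of any episode v none. The only such dichotomy in the protocol is the severe one in Sample Size. Severe episodes are logged continuously, so the model is workable for them. This stands as far as it goes, but it leaves moderate hypoglycaemia without a matching analysis, and the protocol claims power for it.

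A second defence is that section 9 hands detail to a statistical analysis plan. This also stands for model detail. It does not cover an outcome that the protocol itself words in a way its data collection cannot supply.

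A reader might infer several stronger points, which the documents do not support:

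- **That the severe analysis is biased because no follow-up offset is stated.** An offset is ordinary SAP detail. Section 9 excludes missing data in the main analysis, follow-up continues after withdrawal from treatment, and the documents give no difference in drop-out between arms. With equal follow-up the rate ratio is not distorted.
- **That the count model will not be adjusted for baseline.** The protocol is silent on this and does not rule adjustment out.
- **That severe and moderate counts will be added together.** No section proposes it.
- **That the zero-inflated option is an error.** It is offered only if necessary. Preferring another model for excess zeros or overdispersion is largely a matter of taste.

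**Conclusion.** The mismatch is real but confined to moderate hypoglycaemia. The stated two-year count cannot be formed for these episodes, because at most 12 of about 104 weeks (11.5%) are observed. This follows from Table 1 alone, taking two years as 104 weeks and all three windows as complete; missed visits only lower the share.

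No bias magnitude is attached. Any such figure would need follow-up or window completion by arm, and the documents give neither. The severe-episode analysis and its power figure are unaffected, and so is the primary analysis of HbA1c. The point should be fixed, but because the endpoint is secondary and the needed data are already collected, it is not a critical fault.

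**What to change.** In section 9, Secondary Analysis:

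1. Limit the two-year count to severe episodes.
2. Define the moderate outcome as episode counts over the observed 4-week windows at 6, 12 and 24 months, with log days observed as offset, so that a missed or shortened window is not read as a low rate.
3. Analyse the two types separately, each with GEE clustered on course.
4. Include the baseline counts already collected (12-month severe, 4-week moderate) as covariates, in line with what the section does for the linear models.

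An offset for severe follow-up time, and the handling of excess zeros or overdispersion, can be set in the statistical analysis plan.

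The cost is a few sentences in the protocol or SAP and modest programming. No new data, visits or participants are needed. The wording should be settled before hypoglycaemia data are examined by arm.
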